## **Introduction**

Late and long term sequelae following breast cancer treatment, such as lymphedema, affects patients quality of life due to many factors, amongst these are reduced functional ability due to affected shoulder and arm function, emotional problems and negative view on body image following treatment. (1,2)

A growing body of literature shows promising results for reconstructive surgery as a physiological treatment of secondary lymphedema, resulting in a decreased rate of sequelae following breast cancer treatment, such as reduced volume of the affected extremity and episodes of erysipelas, improved quality of life and functionality of the limb. (3–7) However, there is a lack of systematics when it comes to patient characteristics and surgical procedure, which necessitates further studies to address this challenge. Recent research emphasizes the importance of correctly identifying which vessels to anastomose, in order to select the most suitable vessels and patients for treatment; to carefully plan and personalise the treatment plan, based on the patient's physiology. (2,6,8–11)

The primary aim of this study is to investigate and test if we can correctly identify lymphatic vessels and venules in close proximity to each other using combined ICG lymphography and ultra high frequency ultrasonography for identification prior to LVA surgery.

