We therefore wish, based on the knowledge, to add to the knowledge regarding targeted surgical treatment of lymphedema. Hopefully this pilot study that uses a combination of an ICG camera and ultra high frequency ultrasound will enable us to propose an algorithm, that can be used for lymphedema patient, when selecting between surgery and other treatment modalities. Thus, we hope our method helps to specify which patients may benefit from surgery. The primary aim of this pilot study is to investigate and test if we can correctly identify lymphatic vessels and venules in close proximity to each other using a combination of indocyanine green (ICG) lymphography and ultra high frequency ultrasound prior to lymphovenous anastomosis.

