### **Material and methods**

[figure not shown]
ICG lymphography is a technique for visualization of the superficial lymphatic systems. By injecting ICG subcutaneously, it enables a real-time visualization of the lymphatic networks through a minimally invasive procedure. ICG is a non-toxic tracer with low risk of complications; 0.17% risk in general, and 0,02% for nonsevere shock, by intravenous injection. Severe allergic reaction, including anaphylactic shock, affects fewer than 1/10.000 patients. (32,33)

The ICG lymphography is performed and used for visualisation of the superficial lymphatics for preoperative planning, using 0.1 mL ICG (2.5 mg/mL Verdye, Diagnostic Green, Ascheim, Germany). The dye is injected subcutaneously at the wrist, near the ulnar border of the palmaris longus tendon, and in the 1st and 3rd web space of the hand. Scans are performed using an infrared camera, the HyperEye medical system (MNIRC-501, HEMS; Mizuho Co., Tokyo, Japan). During real-time visualization, lymphatic vessels are drawn up on the patients arm using a permanent marker. (32,34)

Ultra high frequency ultrasound (>30MHz) has the ability to visualize small, superficial anatomical layers. (10,30,35) Using this ultra high frequency ultrasound, following the mapped lymphatic vessels, venous vessels are found nearby and likewise mapped for anastomosis. The ultrasound scans are performed using a 70MHz probe (Vevo® MD Imaging System, Fujifilm, VisualSonics Inc.). The number of LVA anastomosis sites is set to a minimum of two sites per extremity. The number of mapped lymphatics vessels and venoles are compared to the number identified during surgery and recorded.

The secondary outcomes includes: 1) changes of arm volume over time, 2) changes of lymphatic flow pattern before and after surgery by ICG lymphangiography, 3) changes in health-related quality of life by the use of the LYMPH-Q questionnaire and 4) changes in L-Dex score and body composition measured with bioimpedance before and 3 months after LVA surgery. (32,36,37,37–39)

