Patients with breast cancer related pitting-lymphedema in one of their upper extremities, who is above the age of 18 and capable of providing informed consent, is included. If pitting edema does not occur, the patient may not be included. However, if the patient's lymphedema has lasted for over 24 months, if she currently is smoking or if there are any untreated or uncontrolled primary breast-cancer, which can cause further damage to the lymphatics and influence the measurements of this study, the patient is excluded from the study, see table 2.

Inclusion criteria:	Exclusion criteria:

 
• Female
 
	
 
• Duration of disease over 24 months
 

 
• Iatrogenic lymphedema following treatment for breast cancer in upper extremity
 
	
 
• Smoker
 

 
• Possible to obtain informed consent
 
	
 
• Untreated or uncontrolled primary cancer
 

 
• Age>18
 
	
 
• No applicable lymphatic vessels identified, using ICG lymphangiography
 

	
 
• No applicable venous vessels identified using ultra high frequency ultrasound
 

*Table 2: Patient inclusion and exclusion criteria.*

Included participants will undergo surgical intervention with LVA, in the affected upper extremity. Prior to surgery, pre-operative mapping of relevant lymph- and venous vessels using respectively ICG lymphography and ultra high frequency ultrasound for visualization, evaluation and selection, will be performed.

During real-time ICG lymphangiography, lymphatic vessels are mapped on the patient's arm, in relation to its dermal backflow pattern. Then, following the mapped lymphatic vessels using ultra high frequency ultrasound, venules will be identified nearby and equally mapped. Videos and pictures of the patient arms and ICG lymphangiography will subsequently be performed.

After detection of applicable vessels per-operatively, the lymphatic vessels and venules will be dissected and anastomosed in a ratio of 1:1.

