### **Collection of Data**

Pre-operative: The patients will be examined in the outpatient clinic by the primary investigator. Circumference tape measurement and water displacement will be executed for volume quantification of both arms, in addition to bioimpedance for measurements of L-Dex score and body composition. A questionnaire regarding quality of life in relation to living with lymphedema, LYMPH-Q, will also be completed prior to the intervention.

ICG lymphography will subsequently be performed by the operating surgeons and the primary investigator for mapping of lymphatic vessels. (33,34)

Ultra high frequency ultrasound will be used for mapping veins adjacent to the lymphatic vessels for anastomosis. The number of vessels and their location for anastomosis will be registered and mapped prior to surgery.

Video recordings of the ICG lymphography is performed for staging of lymphedema. Photos of the patient's arms will be recorded as well.

During surgery: The number of actual applicable lymphatic vessels and venous veins found during surgery will be registered, and also whether these were usable for anastomosis.

3 months post-operative follow-up: Patients will be examined in the outpatient clinic for circumference tape measurement and water displacement for volume calculation of both arms, in addition to bioimpedance for measurements of body composition and L-Dex score, in addition to ICG lymphangiography. The patients will be asked to complete the LYMPH-Q questionnaire once again.

Cases of adverse side effects will be collected continuously.

Collected data provides the following for comparison, as previously described:

- 1) The primary outcome is comparison of the number of lymph vessels and venules found during surgery and the number originally planned.
- 2) Arm-volume measurements for each patient will form the basis for calculating the volume difference between the patient's arms. The volume difference before and after surgery will be compared. This applies to data collected from both manual measurements and water-displacement test.
- 3) Comparison of ICG lymphography video recordings before and 3 months after intervention, with changes in MD Anderson classification system of lymphedema.
- 4) Changes in LYMPH-Q scores for each individual scale from before and 3 months after intervention.
- 5) Changes in L-Dex score measured by stand-up bioimpedance before and 3 months after surgery. (38,39)

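### The primary outcome counts vessels, but the stated aim is correct identification of adjacent lymphatic-venule pairs, and no pair is scored

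*Protocol*

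**What the plan says.** The primary aim appears twice. The Introduction wants to know whether the team can "correctly identify lymphatic vessels and venules in close proximity to each other using combined ICG lymphography and ultra high frequency ultrasonography"; the Background repeats that the study will "investigate and test if we can correctly identify lymphatic vessels and venules in close proximity to each other".

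Mapping and surgery both work in pairs. Under Design and population, "following the mapped lymphatic vessels using ultra high frequency ultrasound, venules will be identified nearby and equally mapped". Collection of Data says the same of the pre-operative step: "Ultra high frequency ultrasound will be used for mapping veins adjacent to the lymphatic vessels for anastomosis". At surgery, "After detection of applicable vessels per-operatively, the lymphatic vessels and venules will be dissected and anastomosed in a ratio of 1:1". Material and methods adds: "The number of LVA anastomosis sites is set to a minimum of two sites per extremity".

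The outcome is a comparison of numbers. Collection of Data, item 1, reads: "The primary outcome is comparison of the number of lymph vessels and venules found during surgery and the number originally planned". Material and methods agrees: "The number of mapped lymphatics vessels and venoles are compared to the number identified during surgery and recorded".

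As for recording, Collection of Data registers vessel number and location before surgery. During surgery it lists the number found and whether they were usable. The Database section adds the number of anastomoses, the operation description, and pictures and videos.

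**The concern.** The aim makes two demands: the identification must be correct, and the lymphatic and venule must lie close together. The outcome states neither.

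Two readings of the count are possible.

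- **Found means found at the mark.** This is the natural reading. The count then gives a confirmation rate for lymphatics and another for venules, but not the share of sites where both were confirmed. A 1:1 anastomosis at the planned site needs both.
- **Found means any applicable vessel found at surgery.** The sentence on detection at surgery under Design and population does not mention the marks, so this reading is not excluded. An unmarked vessel could then make up for a marked one that was not confirmed, and equal numbers would not show correct mapping.

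The section on sample size makes favourable results the basis for a further, formally sized study. It should therefore be clear what a good result on this outcome shows.

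**Working it through.** The protocol gives no sample size calculation or target rate, so there is no figure of its own to reproduce. The check asks how far the counts determine the number of confirmed pairs.

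**Inputs.** 10 patients (Design and population); at least 2 sites per extremity (Material and methods). Assumed: one lymphatic and one venule per site. This gives 10 × 2 = 20 pairs. The rates found are also assumed, since the documents give none.

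**Step 1: found at the mark, counts pooled.** If L of 20 lymphatics and V of 20 venules are found, confirmed pairs lie between max(0, L + V − 20) and min(L, V).

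| L = V | Lower | Upper | Share of 20 |
|---|---|---|---|
| 18 | 36 − 20 = 16 | 18 | 80% to 90% |
| 16 | 32 − 20 = 12 | 16 | 60% to 80% |
| 14 | 28 − 20 = 8 | 14 | 40% to 70% |

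**Step 2: found at the mark, counts compared within each patient.** With m pairs and l and v found, the undetermined width is min(l, v) − max(0, l + v − m). For m = 2 it exceeds zero only at l = v = 1, where the confirmed pairs may be 0 or 1. At 16/20 and 16/20 overall, the range is still 12 to 16 if four patients each miss one lymphatic and one venule. It is exact if no patient does.

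**Step 3: average width, independent misses, 80% found.**

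- Two sites: (2 × 0.8 × 0.2)² = 0.1024 per patient, so 1.02 of 20 pairs.
- Three sites: the width is 1 when l and v are each 1 or 2. (1 − 0.8³ − 0.2³)² = 0.48² = 0.2304 per patient, so 2.30 of 30.
- Four sites: the width is 1 when l and v are each 1 to 3, and 2 when both are 2. (1 − 0.8⁴ − 0.2⁴)² + (6 × 0.8² × 0.2²)² = 0.5888² + 0.1536² = 0.3703 per patient, so 3.70 of 40.

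**Step 4: any vessel counts as found.** Planned = confirmed + not confirmed + unexplored. Found = confirmed + unmarked. Hence found − planned = unmarked − not confirmed − unexplored. A difference of zero says only that these terms cancel. The documents give no rate of unmarked vessels, so the size is unknown.

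**Step 5: why unexplored sites matter.** With assumed figures of 14 pairs confirmed, 2 not confirmed and 4 unexplored, the rate is 14/20 = 70% of mapped pairs but 14/16 = 87.5% of explored pairs. A bare count does not show which of these is meant.

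**The case against.** The strongest case against runs as follows.

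- **The pooled ranges are extremes.** The protocol says number, not pooled total, and patient-level data are held. Within patients the ambiguity at two sites is small: at 90% found it is 10 × (2 × 0.9 × 0.1)² = 0.32 of 20 pairs. At 16/20 and 16/20 with misses placed at random, the full 12-to-16 width needs both sets of four misses to fall singly in the same four patients. The chance that four misses fall in four different patients is 210 × 16 / 4845 = 0.6935, so the chance of the full width is 0.6935² / 210, about 0.2%. This stands, and the pooled ranges should be read as limits, not as expected error.
- **Reading found as any vessel is strained.** Vessels are drawn on the arm, and the outcome refers back to what was planned. This stands in part: the text does not exclude the looser reading, but it is not the natural one and cannot be sized.
- **Counting rules can sit in an analysis plan that is not shown, and pictures, videos and the operation note could support matching later.** This stands only in part. The protocol itself fixes the outcome and lists the items recorded in theatre. An analysis plan cannot supply a match that was never recorded. Later matching might work for some sites, but none is planned. The number of anastomoses does not show that the marked pair was the one joined.
- **It is a 10-patient pilot with no threshold, and separate rates by vessel type are informative.** This is true and limits the consequence. It does not make the outcome measure the aim.

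**Conclusion.** The concern holds. Aim, mapping and anastomosis all concern a lymphatic and venule together, while the primary outcome concerns numbers of vessels. Followed exactly, the plan does not yield the proportion of mapped pairs correctly identified.

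On the natural reading the loss is modest at the two-site minimum: about 1 of 20 pairs undetermined on average at 80% found, and up to 4 of 20 in the worst arrangement at 16/20 of each type. It grows with more sites per patient. These figures assume one lymphatic and one venule per site, and the averages also assume independent misses. On the looser reading the error has no known size.

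This should be fixed. The pilot can run without the change, but its main result would be hard to interpret.

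**What to change.** - Number each mapped lymphatic-venule pair before surgery.
- At surgery, record four yes/no items per pair: site explored, lymphatic found at the mark, venule found at the mark, pair usable.
- Have the team define in writing, before the first patient, what counts as at the mark, including the reference point on the drawn line.
- Make the primary result the proportion of mapped pairs confirmed, displayed as confirmed, not confirmed or not explored, so that unexplored sites are visible and not read as mapping errors.
- Alongside it, report confirmed over explored pairs and the separate lymphatic and venule rates.
- Count unmarked vessels in their own field, and never offset them against misses.
- Use one term for the pre-operative set, which Material and methods and Collection of Data now name differently.

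The cost is four fields per pair, one count per patient, one written definition and a reworded primary outcome. It builds on locations and vessels already registered, and leaves mapping, surgery and care unchanged. The drawbacks are a little more recording in theatre, a judgement on each vessel's position, and possibly a less favourable rate.

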### **Database**

OPEN REDCap – Research Electronic Data Capture, will be applied for a secure storage of all data. REDCap is a worldwide online system developed for non-commercial clinical research. Data will be stored on OPEN's servers in the Region of Southern Denmark. Here, data is entered via an encrypted connection and meets current data protection requirements. The database will primarily be used to enter and store clinical data, as well as a few simple calculations based on these clinical data, for example BMI calculation. Only members of the research group will have access to this database. No contractual agreement that limits this access, is relevant.

As a starting point, the database will exist until the 31st of January 2024. As the study is a pilot study, there is, however, the possibility of extension with the inclusion of several test subjects for further exploratory study.

Objective measured data, as well as any general personal data that does not already appear in the patient journal, will originally be collected by the primary investigator during the examination.

Collected data and data from the patient's record is then transferred to the REDCap database by the primary investigator. Written informed consent for participating in the project, including collecting information from the patient's examination and journal, is obtained at the patients' first consultation in the outpatient clinic. Only patients who provide written, informed consent is enrolled in the project. No data is collected nor known to the researcher prior to this.

The consent gives the trial supervisor, sponsor and sponsor's representatives as well as any control authority direct access to obtain information in the patient's medical record, as part of the implementation of the research project as well as for control purpose.

The LYMPH-Q questionnaire is completed prior-to and 3 months after the intervention on paper form, which is subsequently entered into the REDCap database by the medical student.

Collected data includes the patients name, social security number, age, height and weight, BMI, gender, breast cancer diagnosis, treatment prior to the study in relation with their breast cancer diagnosis, duration and stage of lymphedema in upper extremity, number of mapped and applicable vessels pre- and per-operatively, number of anastomosis made during surgery, number of days of hospitalization, operation description, description of admission, name of the operators, pictures, videos and measurements from before, during and after the surgery, known allergies, medicine list, smoking status and any side effects or complication related to the surgery or 3 months after.

## **Sample size and Statistics**

No statistical methods are applied in evaluating the sample size and power for this pilot study, as it is a hypothesis generating study. (46) In the case of positive results, this pilot study will form the basis for further clinical study with calculation of a relevant population size.

With the previous experience in the research unit with inclusion of 20 lymphedema patients, it is considered realistic to include 10 patients for this pilot study. In addition, there are already three patients referred to the Department of Plastic Surgery, OUH, who has been evaluated as relevant candidates for LVA surgery.

### **Ethics**

The project will be conducted following Good Clinical Practice (GCP), *The Danish Code of Conduct for Research Integrity* and *General Data Protection Regulation (GDPR)*. (47,48)

*The Research Ethics Committee of the Region of Southern Denmark* has been applied for approval for this project, and the study is registered at the region of Southern Denmark.

In this study, personal data will be processed. In this regard, the Data Protection Act and the Data Protection Regulation will be followed.

### **Impact**

We expect this pilot study to provide more knowledge upon the effect of LVA in specific patient characteristics, and form the basis for further clinical investigation of a larger sample size in case of positive results. This will potentially contribute to reduce the incidence of long-term sequela following breast cancer treatments and improve quality of life. Regardless the result, this study will have a clinical value.

### **Economy**

This study will be economically sponsored by The Danish Cancer Society Foundation.

The funding of 120.000 DKK, will cover the one-year salary of the pre-graduate medical student starting 1st of February 2022 till 31st of January 2023.

Funding are paid to a bank account at the institution, where salary is subsequently paid monthly to the student.

Banking information:

Jyske Bank

Reg.no.: 7562 acc.no.: 0001090051

OOUH's SE no.: 30049179

Southern Denmark Region's CVR no.: 29190909

P-no.: 1003309680

Both the Department of Plastic Surgery Odense University Hospital and the medical student have taken the initiative for this study. Neither author of the Department of Plastic Surgery Odense University Hospital has any financial interest in this article. No patients will receive financial benefits from participating in this clinical study.

### **Feasibility**

The pre-graduate student is responsible of writing the protocol for this study, provide necessary funding, participate in patient inclusion and examinations and assist during surgery, carry out the data analysis, and writing the article. The Department of Plastic Surgery OOUH offers office facilities. Both supervisors provide necessary knowledge and experience to conduct this project within one year.

### **Publication Plan**

This study will be conducted as a pre-graduate research study with [name], Stud. Med. as the primary investigator. Positive, negative, and inconclusive results will all be attempted published in an international journal.

